6.14. Subgroup Analyses

6.14.1. Subgroup Analyses for HbA1c

The following subgroups will be analyzed using the efficacy estimand to evaluate consistency of treatment effects on the primary efficacy measure if there are sufficient numbers of patients in each treatment by subgroup (10% in each subgroup level):

- Age (<40 years, ≥ 40 years)
- HbA1c stratum ($\leq 7.5\%$, $> 7.5\%$)
- Patient's personal CGM/FGM use during the study (yes/no)
- Sex (Male or Female)
- BMI (using the median as the cutoff)
- Bolus delivery speed at study entry
- Use of low glucose suspend
- Duration of diabetes (using the median as the cutoff)
- Duration of CSII use (using the median as the cutoff)
- Race
- Ethnicity
- Country
- Region
- Pump model series (500 Series [MiniMed 530G, MiniMed Paradigm Revel, MiniMed Paradigm Veo], 600 Series [MiniMed 630G, MiniMed 640G])

Analyses for HbA1c and change from baseline in HbA1c will be performed using an MMRM model that includes the same fixed effects given for the primary analysis model plus factors of subgroup, 2-way interaction of subgroup and treatment, 2-way interaction of subgroup and visit, and 3-way interaction of treatment, visit and subgroup. The interaction of subgroup and treatment at the primary endpoint (Week 16) will be evaluated to assess the treatment by subgroup interaction. When analyzing HbA1c stratum ($\leq 7.5\%$, $> 7.5\%$) as a subgroup the baseline HbA1c will be not be included as a covariate to avoid confounding.

6.14.2. Subgroup Analyses for Hypoglycemic Events

For documented hypoglycemia based on the thresholds of BG ≤ 70 mg/dL, the following subgroups will be analyzed using data collected from all randomized patients prior to discontinuation of IP through Week 16:

- Age (<40 years, ≥ 40 years)
- HbA1c stratum ($\leq 7.5\%$, $> 7.5\%$)

- Patient's personal CGM/FGM use during the study (yes/no)
- Duration of diabetes (using the median as the cutoff)
- Duration of CSII use (using the median as the cutoff)
- Use of low glucose suspend
- Bolus delivery speed (standard, quick)
- Region

The event rate and incidence will be analyzed using the same model specified in [Table ITRO.6.6](#) with the addition of factors for subgroup, and 2-way interaction of subgroup and treatment. The 2-way interaction will be used to evaluate treatment by subgroup interaction.

6.14.3. Subgroup Analyses for Unplanned Infusion Set Changes

For incidence and rate of unplanned infusion set changes, the following subgroups will be analyzed using data collected from all randomized patients.

- Bolus delivery speed at study entry
- Average of total daily dose during lead-in (using median as the cutoff)

6.14.4. Subgroup Analyses for CGM Data

To assess the glucose control over the course of approximately 3 days of continuous insulin infusion, the duration and percentage of time in ranges (target, hypoglycemia or hyperglycemia) and incremental AUCs after meals from the CGM data, will be summarized for each treatment by patient's bolus delivery speed at study entry. If there are sufficient patients ($\geq 10\%$) within each bolus delivery speed, an analysis will be performed using a MMRM model with treatment with bolus delivery speed and their interaction to assess the treatment by subgroup interaction.

6.15. Interim Analyses and Data Monitoring

No interim analyses are planned for this study. If an unplanned interim analysis is deemed necessary, the appropriate Lilly medical director, or designee, will be consulted to determine whether it is necessary to amend the protocol.

7. Unblinding Plan

This is a double-blind study. LY900014 and Humalog treatment groups will have premeal bolus doses given via CSII. Investigators, patients, and study site personnel will be blinded to assigned dosing regimens throughout the study.

To preserve the blinding of the study, the Lilly study team will remain blinded throughout the study; only a minimum number of Lilly personnel will see the randomization table and treatment assignments before the study is complete.

Emergency unblinding for AEs may be performed through the IWRS. This option may be used ONLY if the patient's well-being requires knowledge of the patient's treatment assignment. Unblinding events are recorded and reported by the IWRS.

If an investigator, site personnel performing assessments, or patient is unblinded, the patient must be discontinued from IP and should remain in the study.

In case of an emergency, the investigator has the sole responsibility for determining if unblinding of a patient's treatment assignment is warranted. Patient safety must always be the first consideration in making such a determination. If the investigator decides that unblinding is warranted, the investigator should make every effort to contact the Lilly clinical research physician/clinical research scientist (CRP/CRS) prior to unblinding a patient's treatment assignment unless this could delay emergency treatment of the patient. If a patient's treatment assignment is unblinded, Lilly must be notified immediately.

8. References

Baghurst PA. Calculating the mean amplitude of glycemic excursion from continuous glucose monitoring data: an automated algorithm. *Diabetes Technol Ther.* 2011;13(3):296-302.

Hirsch IB. Glycemic variability: It's not just about A1c anymore! *Diabetes Technol Ther.* 2005;7(5):780-783.

Appendix 1. Empirical Estimation of Relative Event Rate

Traditionally, Poisson distribution has been assumed to draw inference for the rate of rare events. When the event is rare and the sample size is large, it is known that the overall number of events is approximately from Poisson distribution. However, for some not very rare events such as severe hypoglycemic events in T1D patients, the total number of events may not be distributed from Poisson and may be over-dispersed. Assuming Poisson distribution may significantly underestimate the variance, and therefore may reduce the coverage probability and inflate the Type-I error. An empirical method in estimating the variance of the relative event rate without assuming any distribution on the number of events will be provided in this appendix. Let X_{ij} denote the count response variable for patient j in treatment group i . Let $Y_i = \sum_j X_{ij}$ be the total number of events for treatment group i , and T_i denote the exposure for treatment group i . Let $i = 0$ for the control group and $i = 1$ for the experimental treatment group. The event rate for treatment group i can be calculated as

$$\hat{r}_i = \frac{Y_i}{T_i}$$

The empirical variance of \hat{r}_i is

$$\widehat{Var}(\hat{r}_i) = T_i^{-2} \widehat{Var}(Y_i) = T_i^{-2} n_i S_i^2,$$

where S_i^2 is the variance of X_{ij} for treatment group i . Using the delta-method, the variance of $\log(\hat{r}_i)$ can be estimated as

$$\widehat{Var}(\log(\hat{r}_i)) = Y_i^{-2} n_i S_i^2$$

The relative rate of the experimental treatment versus the control treatment is estimated as

$$\hat{\lambda} = \frac{\hat{r}_1}{\hat{r}_0}$$

The variances of $\hat{\lambda}$ and $\log(\hat{\lambda})$ are

$$\widehat{Var}(\hat{\lambda}) = \hat{\lambda}^2 \widehat{Var}(\log(\hat{\lambda}))$$

$$\widehat{Var}(\log(\hat{\lambda})) = \widehat{Var}(\log(\hat{r}_0)) + \widehat{Var}(\log(\hat{r}_1)) = Y_0^{-2} n_0 S_0^2 + Y_1^{-2} n_1 S_1^2$$

Assuming $\log(\hat{\lambda})$ is asymptotically from a normal distribution, the $100(1 - \alpha)\%$ confidence interval for $\log(\hat{\lambda})$ can be constructed as

$$\left[\log(\hat{\lambda}) - z_{1-\frac{\alpha}{2}} \sqrt{\widehat{Var}(\log(\hat{\lambda}))}, \log(\hat{\lambda}) + z_{1-\frac{\alpha}{2}} \sqrt{\widehat{Var}(\log(\hat{\lambda}))} \right]$$

Then, the $100(1 - \alpha)\%$ confidence interval for $\hat{\lambda}$ is

$$\left[\hat{\lambda} \exp\left(-z_{1-\frac{\alpha}{2}} \sqrt{\widehat{Var}(\log(\hat{\lambda}))}\right), \quad \hat{\lambda} \exp\left(z_{1-\frac{\alpha}{2}} \sqrt{\widehat{Var}(\log(\hat{\lambda}))}\right) \right] \quad (1)$$

The p-value for testing the null hypothesis of $H_0: \lambda = 1$ is calculated as

$$p = 2\Phi\left(\left|\log(\hat{\lambda})\right|/\sqrt{\widehat{Var}(\log(\hat{\lambda}))}\right) \quad (2)$$

Appendix 2. Derivation of CGM Variables

General Derivation Specifications

All CGM variables will be derived for each patient, for each valid CGM day and also overall for baseline, Visit 10 (Week 6-8) and Visit 13 (Week 14-16).

No missing CGM values will be imputed.

Since the CGM values may not be measured at the exact same time for each day for a specific individual patient, due to device changes or gaps in usage, non-overlapping intervals ('buckets') of 5 minutes over 00:00:00 to 23:59:59 (00:00:00 to 00:04:59, 00:05:00 to 00:09:59, etc.) will be used for any derivations requiring time-matched measurements across days within a visit (e.g., mean of daily difference [MODD]).

All CGM glucose derivations will be conducted in units of mg/dL and will be converted to mmol/L by multiplying by 0.0555.

Only readings from valid CGM days (defined in Section 6.13) collected between first dose and last dose of study drug (i.e., open-label Humalog used during the lead-in period or IP used during the treatment period) will be included in derivations, excluding data (if any) that are collected while patients temporarily are off pump or off study treatment.

The between-day variability, overall variability, and duration of hypoglycemia episode will be derived using all data collected across all valid CGM days, regardless of CGM days. For the other CGM variables, first determine the values within each day, then average across days within a visit.

The postprandial excursion related CGM variables (e.g., highest postprandial excursions, iAUC and mean sensor glucose) will be derived based upon the same excursion data.

Glucose in Target Ranges, Hypoglycemia- or Hyperglycemia

The percentage of time within a glucose range (target, hypo- or hyperglycemia ranges) will be calculated as the number of observations within the specified range divided by the number of observations in the time interval (e.g., 24-hour period). The duration (in minutes) within the glucose range will then be calculated as the percentage of time within the glucose range times the length of the period (24 hours, 18 hours, and 6 hours, for the periods of 24-hour, daytime or nighttime, respectively).

For example, if a patient had a total of 15 observations with glucose values <70 mg/dL (3.9 mmol/L) out of a total of 244 observations recorded in a 24-hour period, the percentage of time spent in hypoglycemia during the 24-hour period for this patient will be calculated as $15/244 = 6.15\%$. The duration (in minutes) with hypoglycemia (glucose value <70 mg/dL [3.9 mmol/L]) during this 24-hour period for this patient will be calculated as the percentage times 1440 minutes (24 hours), (i.e., $15/244*288 = 17.7$ minutes).

The percentage and duration in ranges during postmeal periods after the start of meals (MMTT, breakfast, lunch, and dinner) will also be derived.

Incremental Area under the Glucose Curve (iAUC)

iAUC_{0-T} will be calculated as the average value of iAUC on all valid CGM days during that visit with sufficient data to calculate the iAUC_{0-T} (Section 6.13). For each day, iAUC_{0-T} will be calculated as the sum of areas of all individual trapezoids within the time frame according to the formula:

$$iAUC_{0-T} = \sum_{i=1}^k A_i = \sum_{i=1}^k \frac{(G_i - G_0) + (G_{i-1} - G_0)}{2} \Delta t_i$$

where A_i is area of the respective trapezoid, G_i is glucose concentration at a particular time, G₀ is the starting glucose concentration before the start of the meal, Δt_i is the time interval between consecutive CGM values, which should be always 5 minutes unless missing data occur, and k is the total number of intervals within the time frame 0-T, and T could be 1 hr, 2 hr, 3 hr or 4 hr. If the intermediate time points are missing, the next available time point will be used in calculating the trapezoid area. Also since it is possible that G_i < G₀ or G_{i-1} < G₀, A_i could also be negative. G₀, the starting glucose concentration, will be calculated as the average of the CGM values in the time window [-19, 0] mins relative to the start of the meal (at most 3 CGM values); G_k, the last glucose concentration, is defined as the average of the CGM values in the window [0, +14] minutes relative to the last time point of the time frame (at most 2 CGM values). For example, to calculate iAUC_{0-2hr} after the start of breakfast, G_k will be the average of the CGM values in the window [0, +14] minutes relative to the 2 hours after the start of breakfast. The derivation of each iAUC_{0-T} will require that G₀ and G_k values are both available. The derivation iAUC_{0-T} on a specific infusion set wear day, requires that time 0 and time T fall on the same infusion set wear day but allows that the CGM measures in the window [-19,0] for G0 and [0+14] for GT fall on the previous or the next infusion set wear day.

Mean Sensor Glucose Excursions

Mean sensor glucose excursions in a postmeal time interval will be calculated by averaging all excursion values within the time interval where excursions are defined as G_i - G₀ as defined in iAUC.

Hypoglycemic/Hyperglycemic Episodes

Hypoglycemic/hyperglycemic episodes as measured by CGM data are defined as at least 10 consecutive minutes below/above the specified threshold, and determined by 3 or more consecutive CGM values meeting the criterion.

The number of distinct hypoglycemic episodes that start will be derived along with days of CGM use (Section 6.13) to calculate the rate of hypoglycemic episodes during a 24-hour period. For example, the rate of postprandial hypoglycemic episodes (<70 mg/dL [3.9 mmol/L]), during the 24-hour period, will be calculated with the following steps:

- Step 1: identify all events as runs of 3 or more consecutive CGM values meeting the criterion, where the pre-marker glucose value (<70 mg/dL[3.9 mmol/L]). Consecutive implies no gaps in time more than 6 minutes between measurements.
- Step 2: Count the number of distinct events over the 24-hour period.
- Step 3: Calculate rate per month by multiplying count by 365.25/days of CGM use. Days of CGM use will be calculated as the number of observations during the 24-hour period divided by the observation supposed to be measured during the period (288 observations for the 24-hour period).

Glucose Variability

Glycemic variability will be evaluated using the notation below:

i represents a time point within a time period (a 24-hour period, daytime or nighttime)

n represents the number of time points within the time period

k represents a day within a visit

m represents number of days CGM is performed at a visit

$BG_{k,i}$ represents the glucose value at time point *i* on day *k* unless otherwise specified under MAGE definition.

Within-Day Variability

For variables assessing within-day variability, first determine the variability within each day, then average across days within a visit.

Within-day glucose standard deviation (SD) (Hirsch 2005; Rodbard 2009):

$$SD = \frac{1}{m} \sum_{k=1}^m SD_k = \frac{1}{m} \sum_{k=1}^m \sqrt{\frac{\sum_{i=1}^n (BG_{k,i} - \left\{ \frac{\sum_{i=1}^n BG_{k,i}}{n} \right\})^2}{n-1}}$$

Within-day glucose coefficient of variation (CV) (Clarke 2009):

$$CV = \frac{1}{m} \sum_{k=1}^m CV_k = \frac{1}{m} \sum_{k=1}^m \frac{SD_k}{\left(\frac{\sum_{i=1}^n BG_{k,i}}{n} \right)} \times 100$$

Inter-quartile range (IQR) (Mazze et al. 2008):

$$IQR = \frac{1}{m} \sum_{k=1}^m IQR_k = \frac{1}{m} \sum_{k=1}^m (75\text{th} - 25\text{th percentile of all BG values on day } k)$$

Mean amplitude of glycemic excursions (MAGE) (Service et al. 1970, 1987; Baghurst 2011): MAGE is the mean of the excursions between consecutive peaks and nadirs in BG that meet qualifying criteria,

$$MAGE_k = \frac{\sum_{l=1}^p |BG_{k,l} - BG_{k,l-h}|}{p}$$

where,

$BG_{k,l}$ = the low point in consecutive BG time points for the k^{th} day (nadir)

$BG_{k,l-h}$ = the high point in consecutive BG time points for the k^{th} day (peak)

p = the number of qualifying excursions: $(BG_{k,l} - BG_{k,l-h}) \geq 1 SD_k$ and that follow the direction of the first qualifying difference within the BG time points for the k^{th} day.

The peaks and nadirs will be algorithmically (Baghurst 2011; Approach 1), using a variant that removes the proposed and unnecessary first step of using a smoothing function.

Between-Day Variability

For variables assessing between-day variability, first determine the variability for each time points across days within a visit then average across all time points.

Between-day glucose standard deviation (SD) (Rodbard 2009):

$$SD = \frac{1}{n} \sum_{i=1}^n SD_i = \frac{1}{n} \sum_{i=1}^n \sqrt{\frac{\sum_{k=1}^m (BG_{k,i} - \left\{ \frac{\sum_{k=1}^m BG_{k,i}}{m} \right\})^2}{m-1}}$$

Between-day glucose coefficient of variation (CV):

$$CV = \frac{1}{n} \sum_{i=1}^n CV_i = \frac{1}{n} \sum_{i=1}^n \left(\frac{SD_i}{\left\{ \frac{\sum_{k=1}^m BG_{k,i}}{m} \right\}} \right) \times 100$$

Mean of daily differences (MODD): this parameter is calculated as the mean of absolute differences between glucose values at corresponding time points of consecutive days.

$$\text{MODD} = \frac{1}{m-1} \sum_{k=1}^{m-1} \frac{\sum_{i=1}^n |BG_{k+1,i} - BG_{k,i}|}{n}$$

In addition to the CGM outcomes above, SD and CV in the daily mean values will also be derived.

Overall Variability

The CV, SD, IQR, low blood glucose index (LBGI), high blood glucose index (HBGI), and blood glucose risk index (BGRI) will be calculated using the standard formulas across collected across all valid days for time interval in each randomized treatment period.

Risk for Hypo/Hyperglycemia

The LBGI has been developed to quantify both frequency and severity of hypoglycemia. The LBGI has been validated as a predictor of severe hypoglycemia, which is a SAE and could result in coma or death if unrecognized and untreated. The HBGI quantifies both frequency and severity of hyperglycemia and has been related to HbA1c and risk for hyperglycemia (Kovatchev et al. 2005). Additionally, both the LBGI and HBGI have a high sensitivity to changes in glycemic profiles and control (Kovatchev et al. 2005). Low blood glucose index is a non-negative number that increases as the number of low readings increases. High blood glucose index is a non-negative number that increases as the number of high readings increases.

The LBGI, HBGI, and BGRI will be derived for each day of a visit and for overall in the following steps:

Step 1: For each blood glucose (BG [mg/dL]) at the i th time point, compute the following:

$$f(BG_i) = 1.509 \times [(\ln(BG_i))^{1.084} - 5.381]$$

This transforms the BG data using a nonlinear transformation that maps the BG range of 20 to 600 mg/dL to a symmetric interval of $(-\sqrt{10}, \sqrt{10})$

The center of the BG scale is 112.5 mg/dL and is mapped to 0

Step 2: Compute BG risk for each reading

$$rl(BG_i) = 10 \times f(BG_i)^2 \text{ if } f(BG_i) < 0; \text{ otherwise } rl(BG_i) = 0$$

$$rh(BG_i) = 10 \times f(BG_i)^2 \text{ if } f(BG_i) > 0; \text{ otherwise } rh(BG_i) = 0$$

Assign the risk of each BG value by applying the above quadratic risk function

Value range from 0 (achieved when BG = 112.5, the center) to 100

Left side of the parabola is risk of hypoglycemia, and the right side is risk of hyperglycemia

Step 3: Compute LBGI and HBGI

$$LBGI = \frac{1}{n} \sum_{i=1}^n rl(BG_i)$$

$$HBGI = \frac{1}{n} \sum_{i=1}^n rh(BG_i)$$

Step 4: Compute BGRI

$$BGRI = LBGI + HBGI$$

Daily CGM Data Summary

For daily CGM summary variables (Section 6.13), first determine the values within each day, then average across days within a visit. The hourly mean glucose will be calculated as the mean across all CGM values collected, based on actual local time for the subject.

AUC

Area under the curve (AUC) during a period (24-hour, daytime, or nighttime) will be calculated using the standard linear trapezoidal method as defined previously (see section “Incremental Area under the Glucose Curve [iAUC]”) by multiplying the sum of trapezoids by (the length of the period)/ sum of time intervals calculated in the AUC).

Highest Postprandial Glucose

Time from start of meal to the highest postprandial glucose level will be calculated as the time from start of meal to the maximum glucose value within 4 hours after meals, excluding the data from patients who have had the next meal event. If there are multiple time points with the maximum glucose value, then the earliest time will be used.

Highest postprandial glucose level excursions within 4 hours after meals, will be calculated as the maximum glucose value during 0 to 4 hours after start of meal, truncating the data at the next meal event.

Other

The duration of each episode of hypoglycemia will be calculated as stop time – start time.

Leo Document ID = da7d3bbf-504d-42db-90d6-967d07a24b0e

Approver: PPD

Approval Date & Time: 22-Jan-2020 19:08:35 GMT

Signature meaning: Approved

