	Rate (events/patient/year) and incidence (percent of patients with at least 1 event) of hypoglycemic episodes, defined as at least 10 consecutive minutes <54, 54-69 and <70 mg/dL [3.0, 3.0-3.8 and 3.9 mmol/L]	X	X	X	X

Category	Endpoints	24-Hour	Daytime ^a	Nighttime ^b	By Meal ^c
	Duration (in minutes) of hypoglycemic episode (defined as at least 10 consecutive minutes <54 mg/dL [3.0 mmol/L])		across all hypoglycemic episodes with duration at least 10 consecutive minutes		

Abbreviations: AUC = area under curve; BGRI = blood glucose risk index; CGM = continuous glucose monitoring; CV = coefficient of variation; HBGI = high blood glucose index; hr = hour; IQR = interquartile range; LBGI = low blood glucose index; MAGE = mean amplitude of glycemic excursions; MODD = mean of daily differences; SD = Standard deviation.

- a Daytime: 0600 hours to midnight (06:00:00-23:59:59 on the 24-hour clock).
- b Nighttime: midnight to 0600 hours (00:00:00-05:59:59 on the 24-hour clock).
- c By meals: for MMTT, and non-MMTT meals separately. Non-MMTT meals include all outpatient meals including morning (breakfast), midday (lunch) and evening (dinner) meals and overall (average across the 3 meals).
- d Mean sensor glucose measured at different time points (1, 2, 3 or 4 hours) after the start of the meal minus mean sensor glucose at the start of meal
- e Overall variability refers to the variability calculated based upon all the CGM measurements collected across all valid days for each derivation period.
- f In addition, postprandial hypoglycemia episodes during the following time interval after the start of each meal and overall will also be derived: <=1hr, <=2hr, >2 to <=4hr and <=4hr. The calculation will exclude any data collected after the next meal event.

To assess the glucose control over the course of approximately 3 days of continuous insulin infusion, the duration and percentage of time in ranges (target, hypoglycemia or hyperglycemia) and incremental AUCs after meals, will be derived based upon the CGM raw data collected on each of the infusion set wear days, including Day 1 (>0 and \leq 24 hours), Day 2 (>24 and \leq 48 hours), and Day 3 (>48 and \leq 72 hours) and summarized by treatment. In addition, only meals with the entire analysis interval (e.g., 0-1 hour after the start of the meal) on the same infusion set wear day will be included.

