The meal time will be collected in the database by eCRF both for the MMTT and non-MMTT meals. The non-MMTT meals include all outpatient meals including morning (breakfast), midday (lunch) and evening (dinner) meals and overall (across the 3 meals). For the non-MMTT meals, only the first meal marker time will be used for each category (breakfast, lunch or dinner). Any data collected after the next meal (regardless of the category of the next meal) will be censored for the analysis with regards to the current meal. No outcome variables will be derived for bedtime meal but its time will be used to censor the data when deriving outcome variables for dinner. Time in ranges by meal will be derived for 0 to 1 hour, 0 to 2 hours, 0 to 3 hours and 0 to 4 hours after the start of each meal while variability by meal will only be derived for 0-4 hours.

All continuous variables will be analyzed using a similar MMRM model as used for the primary endpoint. If the percentage of patients with baseline missing (potentially due to missing meal event markers) is greater than 20% for any meal, a constrained longitudinal data analysis (cLDA) will be performed for all PPG-related CGM endpoints for that meal with treatment, strata (pooled country and patient's personal CGM use during the study), visit, and 2 dummy variables

to indicate treatment effect of LY90014 relative to Humalog at Visit 10 and Visit 13, respectively. An unstructured covariance structure will be used to model the within-patient errors. Significance tests will be based on LS means and Type III tests. SAS PROC MIXED will be used to perform the analysis. If this analysis fails to converge, the same order of the covariance structures will be tested as specified in Section 6.11.1.

Hypoglycemia/hyperglycemia rate per year as measured by CGM data will be analyzed using a negative binomial regression model with treatment as a covariate and an offset defined as the log transformation of days of CGM use/365.25 days. The proportion of patients with at least 1 hypoglycemia/hyperglycemia event as measured by CGM data (incidence) will be analyzed using a logistic regression model with treatment in the model. Similarly, proportion of patients who have achieved the guidance (Battelino 2019) recommended CGM targets of glycemic control (Table ITRO.6.6) during the 14 to 16 weeks of the treatment period will be summarized by treatment and analyzed using the same analysis methods.

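### SAP Appendix 2 treats the next meal differently for time to peak glucose than for the peak itself and the rest of the CGM plan; two derivations beside it need small corrections

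*SAP*

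**What the plan says.** **Time to peak.** Table ITRO 6.5 of the SAP lists, by meal, the highest glucose within 4 hours and the time at which it occurs. In Appendix 2 (Highest Postprandial Glucose), the timing variable is derived by "excluding the data from patients who have had the next meal event". The following paragraph, on the highest value, proceeds by "truncating the data at the next meal event".

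The other next-meal rules in the SAP are of the second kind:
- Section 6.13, general by-meal rule: "Any data collected after the next meal (regardless of the category of the next meal) will be censored for the analysis" of the current meal.
- Section 6.13, bedtime snack: "its time will be used to censor the data when deriving outcome variables for dinner".
- Table ITRO 6.5, footnote f, on postprandial hypoglycemia: "The calculation will exclude any data collected after the next meal event".
- Section 6.13, ambulatory glucose profile figures: only readings after the next meal are left out.

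**MAGE (Appendix 2).** The first glucose term is defined as the nadir and the second as the peak. The numerator takes the absolute difference. The divisor p is "the number of qualifying excursions", and its criterion is printed as first minus second of at least 1 SD_k, in plain parentheses.

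**iAUC (Appendix 2).** The starting value G0 averages the readings "in the time window [-19, 0] mins relative to the start of the meal (at most 3 CGM values"). The end value averages those in [0, +14] minutes, stated to be at most 2. Readings are 5 minutes apart.

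**The concern.** The time-to-peak sentence is the only next-meal rule in the SAP that conditions on patients rather than on readings. Two programmers could code it in different ways, and under any literal coding the peak and its timing would not describe the same patients or meals. That also sits badly with the general statement in Appendix 2 that postprandial excursion variables are to be derived from the same data.

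The timing of the next meal is known only after randomization, so inclusion would depend on behaviour under treatment. Such events are foreseeable: patients record bedtime snacks during the CGM sessions (Protocol 9.1.4.6), and the SAP already uses them to cut off the dinner window. Time to peak also bears on the product rationale of faster insulin action (Protocol 3.1 and 3.2), so its derivation should be executable without interpretation.

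The MAGE and iAUC items are smaller. One criterion cannot be met as printed, and two stated counts do not fit their windows.

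**Working it through.** **1. Time to peak.** Let q be the chance that another recorded meal or snack starts within 4 hours. The documents give no value, so q is an assumption shown over a range. The session length of 14 days is from the protocol.

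- Read with no time limit, nearly every outpatient meal has a later meal and almost nothing remains. This cannot be the intention.
- Read per patient within 4 hours, one meal category, 14 valid and independent days: patients lost = 1-(1-q)^14.
- Read meal by meal: meals lost = q. A patient disappears only if all 14 days are affected, q^14, which is about 5e-8 at q = 0.30.

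| q (assumed) | meals lost, meal by meal | patients lost, per patient |
|---|---|---|
| 0.05 | 5% | 1-0.488 = 51% |
| 0.10 | 10% | 1-0.229 = 77% |
| 0.20 | 20% | 1-0.044 = 96% |
| 0.30 | 30% | 1-0.007 = 99% |

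If early next meals cluster in habitual snackers, or fewer than 14 days are valid, the last column is smaller for the same average q.

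Truncation by itself removes no patient and no meal. One detail is left open: Section 6.13 requires 70% of expected readings. For 4 hours that is 0.70 x 240/5 = 33.6, so 34 of 48 readings, or about 170 minutes. The SAP does not say whether the expected number is reduced after truncation. Whatever the answer, it would apply equally to the peak and its timing.

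The by-meal variables are also derived for the MMTT. That test lasts 4 hours with no planned second meal (Protocol 9.1.4.7), so its version is largely unaffected unless the rule is read with no time limit.

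**2. MAGE.** Nadir minus peak is at most 0, and SD_k is above 0. The printed criterion is therefore never met, p = 0, and MAGE_k = 0/0. One simulated day (288 readings, SD 35.5 mg/dL) had nadir-minus-peak differences of -95.0, -106.4, -96.5 and -103.1 mg/dL. As printed, 0 of 4 qualify. With an absolute difference, 4 of 4 qualify and MAGE = 401.0/4, about 100 mg/dL.

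**3. iAUC windows.** The plan's sampling grid reproduces: 1440/5 = 288 readings per day and 120/5 = 24 per 2 hours. The stated counts do not.

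- [-19, 0]: 19/5 = 3.8, so 4 readings in about 80% of alignments and 3 in about 20%. Stated: at most 3.
- [0, +14]: 14/5 = 2.8, so 3 readings in about 80% and 2 in about 20%. Stated: at most 2.
- Open, closed and half-open limits, with exact times or times cut to the minute, all leave maxima of 4 and 3.
- [-14, 0] holds at most 3 and [0, +9] at most 2, which matches the stated counts.

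Using 4 rather than 3 pre-meal readings moves their mean time from -5 to -7.5 minutes.

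**The case against.** The best defence is that the time-to-peak sentence is a loose paraphrase of the Section 6.13 rule. That rule is general and covers this endpoint. Appendix 2 derives variables within each day and then averages across days, so a meal on a day is at least as natural a unit of exclusion as a patient. This stands, and it limits what can be claimed:

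- A reader might infer that the endpoint is emptied, or take the 77% to 99% losses as expected. The documents do not support that. Those figures need patient-level exclusion over the whole session and an assumed q, and the MMTT version largely survives either way.
- A reader might infer that eating to treat hypoglycemia makes the exclusion depend on treatment. Carbohydrate taken for that purpose is not described as a meal marker, so the text gives no such mechanism. What remains is selection on a post-randomization event, without evidence that it differs by arm.
- A reader might conclude that MAGE is lost. The absolute value in the numerator, the verbal definition and the cited peak-finding algorithm make the intention clear. The missing bars may be typographical or lost in reading the PDF.
- The iAUC windows can be executed as they stand; the counts are parenthetical. The windows do not always hold 4 and 3 readings: with timing to the second they sometimes hold 3 and 2. Both arms use the same windows, so no bias follows unless premeal slopes differ by arm. If the counts are meant as caps, however, no rule says which readings to keep.

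The defence does not remove the conflict. The sentence says patients, its neighbour says truncate, and the SAP does not say which prevails.

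**Conclusion.** The inconsistency is real and worth removing; its importance is low. Time to peak is governed by a sentence that contradicts the adjacent paragraph and Section 6.13. Followed as written, it selects patients or meals on the timing of the next meal and separates the peak from its timing. The loss ranges from a share q of meals to 1-(1-q)^14 of patients, depending on the reading. It cannot be narrowed further because q is not in the documents.

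The MAGE criterion and the iAUC counts are drafting errors with a clear or easily chosen correction. For iAUC, the documents do not show whether the window or the count is the mistake.

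All of this concerns exploratory CGM measures. The iAUCs over 1 and 2 hours belong to exploratory objective 27, while time to peak and MAGE are not named in any of the 29 listed objectives. HbA1c, the MMTT serum glucose endpoints and the time-in-range objectives over 24 hours and daytime are unaffected.

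**What to change.** In SAP Appendix 2:

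1. For time to highest postprandial glucose, replace the exclusion wording with "truncating the data at the next meal event", so that the peak and its timing use the same readings. While there, say whether the 70% completeness rule counts expected readings before or after truncation.
2. Write the MAGE qualifying criterion as an absolute difference of at least 1 SD_k, matching the numerator.
3. Make the iAUC windows and counts agree: either keep [-19, 0] and [0, +14] and state at most 4 and 3 readings, or keep the counts and use [-14, 0] and [0, +9].

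The cost is a few phrases in one appendix. No new data, design change or change to the tested hypotheses is needed.
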